**E. Medical Events/Adverse Events Definitions and Classifications**

An adverse event is any unfavorable or unintended sign, symptom, or disease associated with the use of the study device, whether or not related to the device. Adverse event is synonymous with complication or medical event. All medical events, regardless of classification, are required to be reported on the Adverse Event Report case report form. The completed Adverse Event Report case report form must be submitted to Sponsor in a timely manner. The Investigator or Designee will also promptly provide Sponsor with any additional requested information required for Sponsor to comply with regulatory requirements. If applicable per their reporting requirements, the Investigator or Designee will also report applicable adverse event(s) to their IRB or EC.

1. Classification of the Event:

Adverse Event (AE)(i):

An Adverse Event is any untoward medical occurrence, unintended disease or injury, or untoward clinical signs (including abnormal laboratory findings) in subjects, users or other persons, whether or not related to the medical device.

Serious Adverse Event (SAE)(i):

A Serious Adverse Event is any adverse event that

- a. led to death
- b. led to serious deterioration in the health of the subject, that either resulted in
  1. a life-threatening illness or injury, or
  2. a permanent impairment of a body structure or a body function, or
  3. in-patient or prolonged hospitalization, or
  4. medical or surgical intervention to prevent life-threatening illness or injury or permanent impairment to a body structure or a body function
- c. led to fetal distress, fetal death or a congenital abnormality or birth defect.

Note: Planned hospitalization for a pre-existing condition, or a procedure required by the protocol, without serious deterioration in health, is not considered a serious adverse event.

Adverse Device Effect (ADE)(i):

An Adverse Device Effect is an adverse event related to the use of a medical device.

Note 1: This definition includes adverse events resulting from insufficient or inadequate instructions for use, deployment, implantation, installation, or operation, or any malfunction of the medical device.

Note 2: This definition includes any event resulting from use error or from intentional misuse of the medical device.

Serious Adverse Device Effect (SADE)(i):

A Serious Adverse Device Effect is an adverse device effect that has resulted in any of the consequences characteristic of a serious adverse event.

Sponsor is responsible for determining the final classification of adverse events.

If an Unanticipated Serious Adverse Device Effect (USADE) is identified by Sponsor, it will be promptly reported to concerned Investigators and regulatory authorities as required by applicable regulatory requirements. If applicable per their reporting requirements, the Investigator or Designee will report the USADE to their IRB or EC.

2. Intensity of Symptoms

Mild:

The subject is aware of the sign or symptom, but finds it easily tolerated. The event is of little concern to the subject and/or little clinical significance. The event is not expected to have any effect on the subject's overall health or well being.

Moderate:

The subject has discomfort enough to cause interference with or change in usual activities. The event is of some concern to the subject's health or well being and may require medical intervention and/or close follow-up.

Severe:

The event interferes considerable with the subject's usual activities. The event is of definite concern to the subject and/or poses substantial risk to the subject's health or well-being. The event is likely to require medical intervention and/or close follow-up and may be incapacitating or life threatening. Hospitalization and treatment may be required.

**NOTE:** The term "severe" refers to the intensity of the event and can be used with any event, without regard to whether or not it meets the criteria for being classified as "serious" or "unanticipated". For example, a subject can have a severe headache, but it is not a serious event.

3. Outcome Definitions

The outcome is in relationship to the Adverse Event, not the treatment rendered for the event (if any).

Resolved:

The adverse event has been resolved and/or no further treatment is required to treat the reported condition or illness.

Tolerated:

The adverse event will most likely never be resolved. The subject "tolerates" the illness or condition as a matter of life.

Pending:

Treatment or diagnostic studies were prescribed for the adverse event and the outcome of the adverse event is not yet known.

Study Withdrawal:

Due to the adverse event, the subject was withdrawn from the study.

Device Removal:

The adverse event resulted in the removal of a study device.

Reoperation of Affected Joint:

The adverse event resulted in reoperation of the study joint, but the reoperation did not include removal of a study device.

Death:

The outcome indicates the subject died as a direct result of the reported adverse event.

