## II. Data Collection Overview

The following table indicates the necessary case report forms to be completed at the given time point:

Form Name	Pre-op	Surgical & Immediate Post-Surgical	6 weeks	6 months	1 year	Years 2, 3, 4, 5 Post-Surgical
Informed Consent	X					
Inclusion/Exclusion Criteria	X					
Demographic Evaluation	X					
Operative Information		X				
Surgical Device Information		X				
Discharge Summary		X				
Physical Exam	X		X	X	X	X
FJS-12 (Forgotten Joint Score)			●	●	●	●
EQ-5D	●		●	●	●	●
KSS - Surgeon completed	X		X	X	X	X
KSS – Patient completed	●		●	●	●	●
Physician Assessment of Post-op Radiographs			X	X	X	X
Adverse Event Report		★	★	★	★	★
Protocol Deviations	★	★	★	★	★	★
Study Completion	★	★	★	★	★	★
Independent Radiographic Review			◆	◆	◆	◆

- X Completed by Investigator or Designee
- Completed by patient
- ★ Completed by Investigator or Designee as applicable
- ◆ Independent radiographic review may be performed by Sponsor’s designee, if applicable at discretion of Sponsor

The following table indicates the necessary case report forms required to be completed for revision patients:

FORM NAME	REVISION (as applicable)	COMMENTS
Physician Assessment of Post-op Radiographs	★	Mark the “pre-revision” exam period.
Adverse Event Report	★	Document adverse event resulting in the revision
Study Completion	★	Complete indicating “Study Prosthesis Removed” under Study Completion Status.

- ★ Completed by Investigator or designee as applicable

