### IV. Study Objectives

The objective of this study is to obtain clinical performance (outcomes) data and survivorship for commercially available *Persona* fixed bearing knee components implanted in primary total knee arthroplasty. This will be done by analysis of validated outcome measurement tools, radiographs and adverse event data.

The assessments will include:

1. Implant survivorship based on removal of a study device
2. Safety based on incidence and frequency of adverse events
3. Clinical performance measured by overall pain and function, quality of life data, radiographic parameters and survivorship

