**B. Clinical Data Collection/Submission**

1. Summary of Case Report Form Data Collection  
Study data will be collected on study-specific Case Report Forms (CRFs) provided by Sponsor. For subjects having bilateral knee replacement, separate case report forms must be completed for each operative side.  
  
The following CRF guidelines should be followed:
  - Complete carefully and accurately.
  - Complete header information consistently across all case report forms for each individual study subject.
  - Use the study subject's initials in header section.
  - Use the study subject's unique Case ID number assigned as instructed.
  - Do not provide information that is not requested on the CRFs.
  - Ensure that all fields are completed. For fields completed by the subject, efforts should be made to obtain any missing responses prior to the subject completing their visit.
2. Data Submission  
Completed CRFs will be submitted directly to Sponsor by electronic data capture and submission via a method approved by Sponsor. Every effort must be made to ensure data submission to Sponsor is made within 30 days of the visit completion.
3. Quality Assurance of Data  
The Investigator should ensure the accuracy, completeness, legibility, and timeliness of the data reported to the Sponsor in the CRFs and in all required reports. Data reported on the CRF, which are derived from source documents, should be

consistent with the source documents or the discrepancies should be explained. All electronic systems used to create, modify, maintain, or transmit electronic study records will be validated according to 21 CFR Part 11(iii). Sponsor will maintain quality control systems, in accordance with Sponsor's policies and procedures.

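### The sponsor's class for each adverse event is final, and the protocol does not require the investigator's view of seriousness and device-relatedness to be recorded or reported beside it

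*Combined protocol and SAP*

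**What the plan says.** Section IX.E.1 (Classification of the Event) defines four classes. The device-related class is given as "An Adverse Device Effect is an adverse event related to the use of a medical device", and its serious form as "A Serious Adverse Device Effect is an adverse device effect that has resulted in any of the consequences characteristic of a serious adverse event". The same subsection then assigns the last word: "Sponsor is responsible for determining the final classification of adverse events". Intensity and outcome follow under separate numbered headings (2 and 3), each with its own scale. There is no corresponding scale for relatedness.

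On capture of events, Section IX.E says: "All medical events, regardless of classification, are required to be reported on the Adverse Event Report case report form". The key to the data collection table in Section II marks that form "Completed by Investigator or Designee as applicable".

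On use of the data, Section IV lists, as one of three assessments, "Safety based on incidence and frequency of adverse events". The Synopsis adds only that complications are summarised by frequencies and percentages. Section XI allows the descriptive summaries to be used in interim reports, regulatory submissions, presentations and publications.

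**The concern.** Whether an event counts as an SAE, ADE or SADE turns on two judgements: is it serious, and is it related to the device. The protocol gives the final decision on both to the company that makes the device. It does not say that the treating investigator's view must be written down, kept as entered, or shown to the reader of a report.

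The study has no control group, so no comparator is classified under the same rule. A lenient or strict rule goes straight into the absolute rate. A confidence interval does not reveal it, because the interval describes sampling error only.

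The class also matters outside the tables. Under Section IX.E.1, prompt notification of an unanticipated serious adverse device effect (USADE) follows when the sponsor identifies one. At stake is the credibility of any device-related or serious-event breakdown, in a study whose summaries may go to regulators or into print.

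**Working it through.** The documents state no ADE or SADE rate, so there is no figure to reproduce. The check is a reading of the text, followed by an illustration of scale.

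**1. What the sponsor's final say covers.** The sentence stands under heading 1 of Section IX.E, after the definitions of AE, SAE, ADE and SADE. It therefore covers seriousness and device-relatedness. Intensity and outcome stand under headings 2 and 3 and are outside it.

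**2. What the protocol sets against it.**
- Investigator's relatedness or seriousness rating: not required anywhere in the text. The Adverse Event Report form itself is not among the documents, so its fields are unknown.
- Rule for disagreement, or a stated reason for a change: none.
- Independent adjudication of adverse events: none. The only independent review is of radiographs, at the sponsor's discretion (Sections II, V and VIII.N).
- Tabulation by the investigator's assessment: none (Synopsis; Section XI.A).

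**3. What is and is not exposed.**
- All-event incidence: not exposed, because every event is reported whatever its class.
- Survivorship: not exposed, because it rests on removal of a study device (Section IV).
- Any SAE, ADE or SADE split: exposed. The plan does not name such rates as outputs, but it defines the classes, so a split is a foreseeable use.

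**4. Scale, by assumption only.** Let p be the rate that investigators would give and d the share that the sponsor downgrades. Then:

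- reported rate = p × (1 − d)
- shift = p × d

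The shift does not contain n, so a larger study does not shrink it. For n, take the Synopsis maximum, 15 × 100 = 1,500 knees, and the Section V minimum of six sites at the per-site cap, 6 × 100 = 600. One reclassified event moves the rate by 100/600 = 0.17 points or 100/1,500 = 0.07 points. Values of p and d are assumed, each event is taken as one knee, counts are rounded to whole events, and intervals are exact (Clopper-Pearson) 95%.

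| n | p | d | events | reported % | 95% CI |
|---|---|---|---|---|---|
| 600 | 2% | 0 | 12 | 2.00 | 1.04–3.47 |
| 600 | 2% | 25% | 9 | 1.50 | 0.69–2.83 |
| 600 | 2% | 50% | 6 | 1.00 | 0.37–2.16 |
| 600 | 5% | 0 | 30 | 5.00 | 3.40–7.06 |
| 600 | 5% | 25% | 22 | 3.67 | 2.31–5.50 |
| 600 | 5% | 50% | 15 | 2.50 | 1.41–4.09 |
| 1,500 | 2% | 0 | 30 | 2.00 | 1.35–2.84 |
| 1,500 | 2% | 25% | 22 | 1.47 | 0.92–2.21 |
| 1,500 | 2% | 50% | 15 | 1.00 | 0.56–1.64 |
| 1,500 | 5% | 0 | 75 | 5.00 | 3.95–6.23 |
| 1,500 | 5% | 25% | 56 | 3.73 | 2.83–4.82 |
| 1,500 | 5% | 50% | 38 | 2.53 | 1.80–3.46 |

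Only in the most extreme case (1,500 knees, 5%, half downgraded) do the intervals before and after fail to overlap.

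A milder case: p = 3.0%, n = 1,500, d = 10% to 30%. The reported rate is 3.0 × 0.9 = 2.7% down to 3.0 × 0.7 = 2.1%, a shift of 0.3 to 0.9 points. The half-width is 1.96 × √(0.03 × 0.97 / 1,500) = 0.86 points. The shift exceeds it only at the top of that range.

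**The case against.** A reader might infer that nothing preserves the investigator's view, and that an event can be downgraded without trace. The documents do not support that. The investigator or designee completes the form, and all events go on it. Section IX.B says "All electronic systems used to create, modify, maintain, or transmit electronic study records will be validated according to 21 CFR Part 11", and requires form data derived from source to be "consistent with the source documents or the discrepancies should be explained". Section IX.C.2 has the site keep study records for at least 2 years, and applicable events go to the IRB or EC where its rules require. The word final is itself consistent with an earlier classification at the site, and the unseen form may already hold one. These points stand. They do not close the gap: such controls preserve what was entered, but the protocol does not require this judgement to be entered, and none of them puts a disagreement before the reader of a report.

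A reader might also infer that only the sponsor's class will reach the safety tables. The plan does not say so; it names no source of classification.

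Other points on that side also stand:
- The study is descriptive, post-market and classed as minimal risk, with no safety hypothesis.
- Some seriousness criteria, such as death and hospitalisation, leave little room for judgement, so the main exposure is relatedness.
- A sponsor may upgrade as well as downgrade; the table above assumes downgrades only.
- The 1,500 knees are a ceiling, not a target.

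These limit the weight of the point but do not remove it.

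**Conclusion.** The point holds in a limited form. The manufacturer decides finally on seriousness and relatedness, and the protocol neither requires the investigator's assessment beside that decision nor provides an independent check. A device-related or serious-event breakdown drawn from this study would rest on one interested party's judgement.

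The size of any effect cannot be determined. The figures above show what assumed rates and downgrade shares would do; they are not evidence that reclassification will occur or in which direction. The conclusion rests on the protocol text alone and would soften if the Adverse Event Report form already captures both judgements from the investigator. Even then, the reporting gap would remain. The change is worth making: it is cheap and does not touch patient care.

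**What to change.** Amend the sentence on final classification in Section IX.E.1 to say that:

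1. The investigator records seriousness and device-relatedness for each event on the Adverse Event Report, and that entry is kept unchanged.
2. The sponsor records its own classification in a separate field and keeps its role in identifying USADEs.
3. Every difference between the two is listed with the sponsor's reason.
4. Any SAE, ADE or SADE table shows both assessments.

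Showing both is enough; a rule that merges them into one headline figure is not needed.

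Cost: up to two data fields (fewer if the form already has them), one extra table, one listing, and a protocol amendment with IRB or EC approval where required (Section IX.D.9). No extra staff are needed. Displayed device-related rates may be slightly higher than under the sponsor's classification alone.

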#### **F. Monitoring of the Study**

Prior to initiating the clinical study, Sponsor will conduct a site initiation visit to ensure the Investigator(s) and study staff understand the study protocol and requirements and have adequate time and resources to implement and conduct the study. Prior to study initiation, the Investigator must have a fully executed CTA and IRB or EC approval of the study protocol and the study Informed Consent.

During the course of the study, Sponsor will conduct periodic central monitoring and maintain contact with the study staff to monitor compliance and evidence of adverse events, in accordance with Sponsor's policies and procedures. Sponsor will address any identified non-compliance with the executed CTA, study protocol, and applicable regulatory requirements.

If onsite monitoring visit(s) are deemed appropriate by Sponsor, the Investigator will permit representatives of Sponsor's monitoring team to have direct access to inspect all source data/documents, study documents/binders, study subject case report forms, corresponding sections of study subject medical/hospital records, and any other documents relevant to the study. All Sponsor visits (including site initiation) will be documented using the Site Monitoring Visit Log (Appendix C).

### **X. Risk Analysis**

This post-market clinical study is classified as minimal risk(iii) and there are no anticipated risks specific to study participation other than the potential loss of confidentiality. There are no experimental procedures in this study, and participation in this study is not anticipated to affect the medical treatment of enrolled subjects.

When used in accordance with product labeling, the risks associated with the use of *Persona* knee components are similar to those of standard, metal-on-polyethylene knee systems used for the same clinical indication or purpose. These risks are categorized below as either general surgical risks or risks associated with the total knee arthroplasty procedure/study device. Unanticipated adverse events can also occur.

#### **A. General Surgical Risks**

General surgical risks and post-operative adverse events can occur with any surgery and include, but are not limited to:

- Anesthetic complications/reactions
- Bleeding and/or excessive blood-loss
- Transfusion reaction
- Chronic Pain
- Post-operative infection
- Vascular injury
- Delayed wound healing
- Deep vein thrombosis (DVT)
- Nerve injury
- Death

**B. Risks Associated with Total Knee Arthroplasty Procedure/Study Device**

Potential adverse events associated with total knee arthroplasty include, but are not limited to:

- Wear of the polyethylene articulating surface
- Progressive bone resorption (osteolysis) as a result of foreign-body reaction to wear debris
- Loosening of the prosthetic knee components
- Fracture/damage of the prosthetic knee components
- Soft tissue impingement or damage
- Dislocation and/or joint instability
- Malalignment of the prosthetic knee components
- Bone fracture
- Nerve damage
- Swelling
- Infection
- Leg length discrepancies
- Poor range of motion
- Delayed wound healing
- Temporary or permanent neuropathies
- Pain
- Cardiovascular disorders including venous thrombosis, pulmonary embolism, or myocardial infarction
- Histological reactions resulting in inflammation
- Metal sensitivity
- Corrosion of metal components (the significance and long-term implications are uncertain and await further clinical evidence and evaluation)

**Minimization of Risk**

Investigators should refer to the package insert for additional information and instructions.

**XI. Statistical Considerations**

Performance of commercially available *Persona* fixed bearing knee components in primary total knee arthroplasty will be evaluated for pain, function, quality of life, and survivorship. Data collected in this study will be summarized descriptively and descriptive summaries will be the basis of any study reports issued. These summaries may be used for interim study reports and may also be used to support regulatory submissions, presentations, and/or publications. Additional surgical technique and instrumentation data may be collected and evaluated.

**A. General Statistical Methods**

Statistical methodology will consist of summarizing collected data descriptively. Categorical data (e.g., gender or race) will be summarized using counts and percentages, and 95% Confidence Interval (CI), over the time periods of interest. Continuous data, such as age, will be summarized by using means, medians, standard deviation, minimum, maximum, and 95% CI over the time periods of interest. Implant survival and return to function will be

summarized using a Kaplan-Meier method and presented with rates (as percentages) and confidence intervals.

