#### **2. Adverse Events**

An adverse event is any unfavorable or unintended sign, symptom, or disease associated with the use of the study device, whether or not related to the device. Adverse event is synonymous with complication or medical event.

See Section IX, Subsection E of this protocol for additional information regarding adverse event classifications. All medical events, regardless of classification, are required to be reported on the Adverse Event Report case report form. The completed Adverse Event Report case report form must be submitted to Sponsor in a timely manner. The Investigator or Designee will also promptly provide Sponsor with any additional requested information required for Sponsor to comply with regulatory requirements. If applicable per their reporting requirements, the Investigator or Designee will also report applicable adverse event(s) to their IRB or EC.

3. Revision

In the event that removal of one or more of the study knee components is necessary, the Investigator will determine the best treatment and/or revision method for the subject.

Prior to revision surgery, the Investigator or qualified Designee must document any significant radiographic findings related to the need for revision on the Physician Assessment of Postop Radiographs case report form. An Adverse Event case report form must be completed for those findings indicated by an asterisk on the Physicians Assessment of Postop Radiograph case report form.

Once the revision surgery has been completed, the Investigator or qualified Designee must complete an Adverse Event case report form as well as a Study Completion case report form terminating the subject from the study. For the study completion status, select “Study Prosthesis Removed”. This procedure also applies to partial revisions such as polyethylene exchange.

4. Investigator Withdrawal

The Investigator can choose to withdraw a subject from the study if the subject no longer meets study inclusion/exclusion criteria. The reason for the Investigator’s withdrawal of the subject must be documented on the Study Completion case report form.

5. Subject Withdrawal

Study subjects may choose to withdraw from the study at any time, for any reason. If possible, a final evaluation will be completed for any subject who no longer wishes to participate in the study. The reason for the subject withdrawal must be documented on the Study Completion case report form.

6. Lost to Follow-up

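### Radiographic findings have no method of their own; if the generic percentages are applied visit by visit, they describe unrevised knees and understate the cumulative risk of findings that lead to revision

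*Combined protocol and SAP*

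**What the plan says.** Section IV makes films part of the performance assessment: "Clinical performance measured by overall pain and function, quality of life data, radiographic parameters and survivorship". The Synopsis lists them in the same way. Section VIII.N requires films at seven visits (6 weeks, 6 months, and years 1 to 5), each read and recorded by the investigator.

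The opening of Section XI omits them. It says performance "will be evaluated for pain, function, quality of life, and survivorship". XI.A then gives one rule for categorical data: "Categorical data (e.g., gender or race) will be summarized using counts and percentages, and 95% Confidence Interval (CI), over the time periods of interest". No denominator is defined, and no sentence is specific to radiographs.

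For a knee that is to be revised, the revision table in Section II gives this instruction for the radiograph form: "Mark the “pre-revision” exam period". Section IX.D.3 (Revision) says that the investigator or designee "must document any significant radiographic findings related to the need for revision on the Physician Assessment of Postop Radiographs case report form". After the operation the site "must complete an Adverse Event case report form as well as a Study Completion case report form terminating the subject from the study". Partial revisions are handled in the same way: "This procedure also applies to partial revisions such as polyethylene exchange".

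**The concern.** A knee whose film shows loosening or osteolysis is more likely to be revised. Once revised, it contributes no film to any later visit. Its last and most informative film carries a label that belongs to none of the seven scheduled visits. Leaving the visit table is therefore caused by the outcome that the table is meant to show, and the distortion favours the device.

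A low percentage at year 5 could mean that few knees developed the finding, or that those which did had already been revised. A plain visit table cannot separate the two. Section XI says that the descriptive summaries are the basis of study reports and may support regulatory submissions and publications. The study has no control group against which an understated figure would stand out.

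**Working it through.** **Step 1: the plan's own figure.** There is none to reproduce. The documents state no radiographic rate, no expected survival and no share of affected knees that come to revision. The numbers below are illustrations on assumed rates.

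**Step 2: a single visit.** Let *f* be the share of implanted knees that develop the finding by 5 years, and *q* the share of those revised before the 5-year film. Of *N* knees, *Nf(1−q)* still show the finding and *N(1−fq)* are still in follow-up. Hence

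visit percentage = *f(1−q) / (1−fq)*, and cumulative percentage = *f*.

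*N* cancels, so the sample size plays no part. With *f* = 3%:

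- *q* = 0: 0.03/1 = 3.0%
- *q* = 0.5: 0.015/0.985 = 1.52%
- *q* = 0.8: 0.006/0.976 = 0.61%
- *q* = 1: 0%

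Other assumed values of *f*:

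| *f* | *q* = 0 | *q* = 0.5 | *q* = 0.8 | *q* = 1 |
|---|---|---|---|---|
| 2% | 2.0% | 1.01% | 0.41% | 0% |
| 5% | 5.0% | 2.56% | 1.04% | 0% |
| 10% | 10.0% | 5.26% | 2.17% | 0% |

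The understatement is nil at *q* = 0, about two-fold at 0.5 and about five-fold at 0.8. For any fixed *q* below 1, the visit percentage rises with *f*.

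**Step 3: all seven visits.** Assume a constant annual hazard *h* of a new finding. A share *a* of new findings is revised before the next scheduled film. Knees already seen with the finding are revised with annual probability *r*. Death and loss to follow-up are left out. The cumulative figure at 5 years is 1 − exp(−5*h*): 4.88% for *h* = 1% and 18.13% for *h* = 4%. The year-5 visit percentages are:

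| *a* | *r* | *h* = 1% (cumulative 4.88%) | *h* = 4% (cumulative 18.13%) |
|---|---|---|---|
| 0 | 0 | 4.88% | 18.13% |
| 0 | 0.5 | 1.92% | 7.52% |
| 0.5 | 0 | 2.50% | 9.97% |
| 0.5 | 0.5 | 0.97% | 3.91% |
| 1 | 0.5 | 0% | 0% |

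Two things follow. First, the second row shows understatement even when every finding is first seen on a scheduled film, because those knees leave later. Second, with *a* = *r* = 0.5 and *h* = 1%, the visit percentage climbs from 0.06% at 6 weeks to 0.97% at year 5. Raising *h* four-fold raises the year-5 figure about four-fold (3.91/0.97 = 4.0). The visit figure still responds to failure; it is just too low as a measure of cumulative risk.

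**The case against.** The strongest reply is that the plan is silent here, not wrong. XI.A is a generic sentence whose examples are gender and race, and its time periods need not be the scheduled visits; a cumulative 0-to-5-year period would also fit. That stands, so the point is conditional on visit-by-visit use.

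A reader might infer that the pre-revision films are collected and then left unused. The documents do not support that. No passage excludes them, and the visit windows in VIII.L run without a gap from day 17 to day 2007, so a dated film in that range could be assigned to an interval. But no rule says that it will be, and the assignment would restore the finding to one interval only. The knee would still be missing from every later visit.

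A reader might also infer that failures disappear from the study's reports. They do not. Removals, including polyethylene exchanges, enter the Kaplan-Meier analysis of survivorship, which XI.B names as the primary endpoint. An Adverse Event form is mandatory for every revision and for asterisked radiographic findings (VIII.N, IX.D.3), and the Synopsis summarises complications by frequency and percentage. Neither route replaces the missing summary. Kaplan-Meier counts removals for any reason and omits affected knees that are never revised. The adverse event summary has no stated denominator or time basis.

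Finally, prevalence among knees still in place is a legitimate descriptive quantity if it is labelled as such. That is why the fix keeps it.

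**Conclusion.** The concern holds in a limited form. Section XI gives radiographic findings neither a method nor a denominator. Under the only rule that fits, applied per visit, the result is prevalence among unrevised knees with a film, which understates the cumulative risk of findings that lead to revision.

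The direction is clear, but the size cannot be computed from the documents. It depends wholly on the share of affected knees revised before the film in question: with 3% affected, the 5-year visit figure is 3.0%, 1.5% or 0.6% for shares of 0, 50% and 80%. All of these inputs are assumptions.

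It would be tempting to go further and say that visit percentages fall toward zero however many knees fail. That is true only in the limit where every affected knee is revised before its next scheduled film. Short of that, findings on scheduled films and in unrevised knees still count.

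The matter concerns one performance domain in a descriptive study, and the primary endpoint is not affected. It is worth correcting because the data are already collected and the correction is cheap.

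**What to change.** Add to XI.A a paragraph to this effect:

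> For each significant finding on the radiograph form, the cumulative incidence of first detection by each scheduled visit will be estimated over all implanted knees, with a 95% confidence interval. Findings on pre-revision films count at their own days post-op. The estimator will allow for incomplete follow-up (for example Aalen-Johansen). Device removal without the finding, and death, are competing events. Prevalence at each visit will be shown alongside, labelled as applying to unrevised knees with a film at that visit.

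The paragraph should list the findings that count as significant and say that the time used is that of detection, since onset between films is not observed.

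No new films, forms or readers are needed. The cost is agreeing the list, deriving a first-detection date for each finding, and a small amount of extra analysis. The figures will look less favourable than visit prevalence alone.
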